Cover Page

Study Title: Rotational Thromboelastometry for the Transfusion Management of Postpartum Hemorrhage After Vaginal or Cesarean Delivery

NCT03064152

April 22, 2021

SUBJECT ENROLLMENT

Patients who meet eligibility criteria will be identified by the investigators. Their obstetricians will be asked whether we may approach the patients prior to hospital admission. With this permission, eligible patients may be approached in person or by phone by a research assistant (non-physician) or a co-investigator (licensed physician) informed about the study, and a recruitment letter and consent form will be given to the patients for review. This will occur in person, by mail (at a patient's request), or upon arrival on labor and delivery. With these methods, subjects will be provided ample time to consider participation in the study. Patients who have been provided the recruitment letter and consent form prior to admission will then be approached when they are admitted to the hospital.

Informed consent will be obtained from all subjects prior to enrollment after a thorough explanation and discussion of the study plan with the physician investigator. Subjects will be given the opportunity to ask any questions and will be encouraged to discuss their decision to participate with any of their treating physicians. Following satisfactory completion of the above noted recruitment procedures, subjects will be consented by the principal investigator or physician co-investigator at least two hours prior to the patient's vaginal or cesarean delivery on the labor floor or in the triage/pre-operative area of the Center for Women and Newborns.

This study will only be conducted in women. Minorities will be approached with the use of available translators for non-English speaking subjects. No other vulnerable populations will be specifically targeted, nor will any one group bear a disproportionate share of the burdens or benefits of the research.

STUDY PROCEDURES

Patient's providers will first approach them to evaluate their willingness to participate in the study by providing the patient with a study information letter with an 'opt out' mechanism. Subjects will then be approached. Subjects will then be assessed for study eligibility as described above. Eligible and consenting patients who experience PPH will then be randomized to "control" or "ROTEM" groups by a computer generated randomization scheme. The obstetrician, nurse, and anesthesiologist involved in the cases will not be blinded to the study solution assignments. An investigator not involved in the case will conduct ROTEM measurements at any time standard coagulation labs are sent.

The management of PPH can occur in the OR or in the labor room. If a patient hemorrhages after vaginal delivery, we do occasionally draw a PPH lab panel [and study lab for a randomized patient] in the labor room. Many times, these patients are then transported to the operating room for further management. The ROTEM device is stationed between labor ORs 3 and 4. A patient sample in a blue vacutainer tube is taken to the ROTEM device from the labor room or the OR, by a co-investigator. At the time of hemorrhage recognition, a blue top and a purple top are drawn and sent to central lab (for any patient, in the study or not). Study patients have one additional blue top drawn for their ROTEM test. By collecting the study sample at the same time our routine samples are sent, study-specific intervention (new IV access solely for study purposes) is avoided. At maximum, we will draw less than 1 tablespoon extra blood for ROTEM® testing during the entire course of this research study. Patients will receive standard of

care for labor and delivery, cesarean delivery, and postpartum care. Patients admitted for delivery at Brigham and Women's Hospital have baseline labs drawn as standard of care. Baseline labs include: type and screen, serum hemoglobin, platelet count, fibrinogen, activated partial thromboplastin time (aPTT), prothrombin time (PT), and red top test.

Transfusion will be based on standard of care utilizing clinical criteria of hemodynamics (noninvasive blood pressure, heart rate, arterial line if deemed clinically useful) and coagulation labs (PT, aPTT, fibrinogen, complete blood count, red top test) in both groups. In addition to standard of care, additional ROTEM blood assays will be performed at any time routine coagulation labs are sent. Providers in the control group will be blinded to ROTEM results. Providers in the ROTEM group will receive real-time ROTEM results and a previously validated ROTEM-based transfusion algorithm for PPH (Mallaiah et al 2015). The investigator will quantitatively measure blood loss during the vaginal or cesarean delivery using a previously validated method (Triton System, Gauss Surgical Inc. Los Altos, CA). The total intravenous fluids given from start to conclusion of the study period will be recorded. The use of vasopressors, uterotonic agents, and antiemetic agents will be recorded.

Study Endpoints

Early Endpoints

Two definitions of early endpoints will be utilized:

1. Subject decision for withdrawal from participation at any time.
2. Any operative or medical condition changes prior to or during the entire study period deemed unacceptable by the obstetrician, anesthesiologist, or physician investigator.

Primary Endpoint

1. Number of blood products transfused, t_0 = diagnosis of PPH by criteria defined above; $t_{\text{final}} = 48\text{h}$ after onset of PPH.

Secondary Endpoints

1. ROTEM values drawn at the time of the last blood sampling within 4 hours from leaving the operating room or within 4 hours from the last blood transfusion, whichever occurs later.
2. Intraoperative blood loss (visual estimate in suction canister and sponges, EBL, and pre- vs post-delivery hemoglobin values).

Maternal morbidity: admission to the intensive care unit postpartum, need for additional postoperative procedures for bleeding, hysterectomy, postoperative infection, transfusion reaction, acute kidney injury, hypovolemic shock, vasopressor requirement, or mortality. Patient records at the 6-week postpartum visit will be reviewed for any incidence of delayed hemorrhage after hospital discharge.

All clinical and other data obtained during this study will be considered confidential. Procedures to limit access to subject charts and information from the study will be in place. The names of study participants will be known only to the investigators. No information regarding the identity of individual subjects will be utilized for publications.

Outcomes considered serious adverse events including hemodynamic instability requiring epinephrine or norepinephrine or resulting in loss of consciousness or cardiovascular collapse, or allergic or anaphylactic reactions may all fit the criteria for withdrawal from the study. Each of these events will warrant an evaluation by the PI; please see “monitoring section” below.

Subject Costs

There will be no costs to the subjects related to the conduct of this study, as there are no additional medications or tests that are not already the routine standard of care at Brigham and Women’s Hospital. ROTEM testing used in the study group will be performed by qualified obstetric anesthesiology physicians under the supervision of a certified lab director, with funding from the department of Obstetrics and Gynecology. Otherwise, subjects and/or their insurance companies will be responsible for the routine medical and surgical procedures and care associated with their cesarean delivery or vaginal delivery and hospitalization.

BIOSTATISTICAL ANALYSIS

ROTEM values between the control and ROTEM groups will be compared as quantitative outcomes against pre-established ranges for each value in pregnancy and choice of product transfused with or without the ROTEM protocol will be compared.

Sample size calculations for the primary outcome of number of blood products transfused is based on a surrogate finding of reduction in transfused products in a matched study population that was demonstrable using 50 subjects per group). We anticipate that by recruiting the same number of patients as in this previous study (100 patients total), we will reproduce the effects of reducing blood product transfusion. A group size of $n = 50$ will give a power of 80% ($\beta = 0.2$) based on a 5% significance ($\alpha = 0.05$); 100 subjects per group will be recruited with the goal of completing 50 subjects in the control group and 50 subjects in the ROTEM group.

Data will be analyzed using one-way analysis of variance and Kruskal-Wallis tests as appropriate. Analysis of variance will be used to compare intergroup demographic data, estimated blood loss (EBL), ROTEM values, and hemoglobin values. All statistical analyses will be performed using Statview v 5.0 for Macintosh. A P value < 0.05 will be considered significant and all data will be reported as mean \pm standard deviation.

Note: the study was stopped prior to our goal enrollment of 100 patients (N = 50 per group). Our total recruitment was N = 49; 26 control, 23 ROTEM due to slower than anticipated recruitment (3 years and 1 month). The decision to stop the trial early was not out of concern for patient safety or adverse events. We are aware that trials stopped earlier than anticipated may dramatically overestimate the effect of an intervention. However, given our lack of impact on our primary outcome in the intervention group we can infer that additional recruitment would yield results of the same clinical outcome (no effect).

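### Hemoglobin change is filed as a blood-loss measure although red cells given also move it, and no outcome is named as a check on whether fewer products left women more anemic

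*Combined protocol and SAP*

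**What the plan says.** Under Study Endpoints, the primary endpoint is "Number of blood products transfused", counted from the diagnosis of PPH to 48 hours after onset. It is a plain count of all products, with no condition on whether replacement was adequate. The Biostatistical Analysis section makes the wanted direction explicit: "we will reproduce the effects of reducing blood product transfusion".

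Secondary endpoint 2 is intraoperative blood loss. It has three listed components: a visual estimate, EBL, and "pre- vs post-delivery hemoglobin values". No time is given for the post-delivery sample. By contrast, the primary endpoint has its 48-hour window and secondary endpoint 1 (ROTEM values) has a 4-hour rule.

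The Biostatistical Analysis section lists hemoglobin as its own comparison: "Analysis of variance will be used to compare intergroup demographic data, estimated blood loss (EBL), ROTEM values, and hemoglobin values". It does not say what a difference in hemoglobin would mean.

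Two other items bear on the point. Study Procedures has the investigator measure blood loss with a validated quantitative device and record total intravenous fluids. The morbidity list includes "admission to the intensive care unit postpartum, need for additional postoperative procedures for bleeding, hysterectomy", and also "acute kidney injury, hypovolemic shock, vasopressor requirement, or mortality", but no test for these outcomes is named.

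**The concern.** A count of products falls when unneeded products are avoided, and it also falls when needed ones are not given. A reader of a positive result would want to know which had happened. For red cells, the most direct laboratory value on record is hemoglobin after delivery.

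The endpoint list gives that value a different job. As a measure of blood loss, hemoglobin change is confounded by the primary outcome: red cells are among the products counted, and they raise hemoglobin. If one arm receives fewer of them, its hemoglobin component points to heavier bleeding even when bleeding is the same. At stake are a blood-loss endpoint that the intervention itself can bias, and a safety question that the collected data could partly answer but that no outcome is assigned to answer.

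**Working it through.** **The plan's own figure.** The plan states 80% power at 5% significance with 50 per group for the product count. It gives no effect size or SD, so this cannot be reproduced. Solved backwards (two-sided, normal approximation), it implies d = √(2/50) × (1.960 + 0.842) = 0.56 SD. This concerns the product count only; the plan gives no figure for hemoglobin.

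**Direction of the bias.** Write hemoglobin change as (red-cell units × rise per unit) − (effect of bleeding) − (effect of dilution by fluids). With bleeding and fluids equal between arms, the arm difference reduces to −(units fewer) × (rise per unit). It is zero only if red-cell use is equal. Read as blood loss, a negative value means more bleeding.

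**Size.** Inputs:
- Group sizes: 50 and 50 (planned), 26 and 23 (achieved), both from Biostatistical Analysis.
- Rise per red-cell unit: 1.0 g/dL (range 0.7 to 1.3). This is an assumption.
- SD of hemoglobin change: 1.5 g/dL (range 1.2 to 2.0). This is an assumption.
- Red-cell difference: half a unit or one unit fewer per woman in the ROTEM arm. This is an assumption; no part of the documents supports either value.

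One-way ANOVA with two groups is the two-sided t test. With d = units × rise / SD, the noncentrality is d / √(1/n₁ + 1/n₂). The critical t is 1.984 on 98 df and 2.012 on 47 df. Here √(1/50 + 1/50) = 0.200 and √(1/26 + 1/23) = 0.286. Probabilities come from the noncentral t distribution.

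| Units fewer | Rise / SD (g/dL) | d | 50 and 50 | 26 and 23 |
|---|---|---|---|---|
| 0.5 | 1.0 / 1.5 | 0.33 | 38% | 21% |
| 0.5 | 0.7 / 2.0 | 0.175 | 14% | 9% |
| 0.5 | 1.3 / 1.2 | 0.54 | 76% | 46% |
| 1.0 | 1.0 / 1.5 | 0.67 | 91% | 63% |
| 1.0 | 0.7 / 2.0 | 0.35 | 41% | 22% |
| 1.0 | 1.3 / 1.2 | 1.08 | nearly 100% | 96% |

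Each entry is the chance of a significant hemoglobin difference when bleeding is identical.

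**What 49 women can show about safety.** The 95% CI half-width for the arm difference at 26 and 23 is 2.012 × 0.286 = 0.58 SD. For an assumed SD of 1.0 to 2.0 g/dL that is 0.58 to 1.15 g/dL. At SD 1.5 it is 0.86 g/dL, wider than the 0.5 g/dL expected from half a unit fewer at 1.0 g/dL per unit. A non-significant result would therefore leave a deficit of that size open.

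**The case against.** A reader might infer that women left more anemic would be reported as a saving in products together with an increase in bleeding. The documents do not fix that outcome. The analysis section compares hemoglobin apart from EBL, so a lower mean would be visible as a hemoglobin difference. No composite is defined, and hemoglobin is not converted to a volume. With equal bleeding, the device measurement should show no systematic arm difference and would count against a bleeding explanation. This stands, with a limit: the device appears only as a procedure. Secondary endpoint 2 does not name it, the documents do not say that EBL means the device value, and no rule says which component prevails if they disagree.

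A reader might also infer that nothing collected bears on adequacy of transfusion. That is too strong. The morbidity list covers several possible consequences of under-transfusion. End-of-bleed ROTEM values, which the plan compares with pregnancy ranges, bear on products other than red cells. What remains is that none of these is named as the check. The documents give no event rates, so whether morbidity could show a modest deficit cannot be calculated from them.

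The mechanism covers red cells only. ROTEM is a coagulation assay, both arms keep hemodynamics and blood count among the transfusion criteria, and nothing in the documents says that the algorithm lowers red-cell use. A fall confined to other products would leave hemoglobin unaffected by this route. This stands, and it makes every figure above conditional.

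Finally, the closing note reports no impact on the primary outcome, so the feared saving was not claimed. But an unchanged total can hide fewer red cells and more of another product, and the plan itself intends to compare choice of product. Nothing shows that such a shift occurred.

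**Conclusion.** The concern holds as a fault of classification and timing. Hemoglobin change is an untimed component of the blood-loss endpoint, is confounded there by red cells and fluids given, and is given no other meaning; no outcome is named as a check on whether a lower product count left women more anemic. The documents do not support the stronger statements that the plan would report more bleeding, or that it has no data on adequacy.

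The classification point needs no numbers. Its practical size does, and rests on assumed values for rise per unit, SD and red-cell difference. At the achieved 26 and 23, the chance of a significant hemoglobin difference at equal bleeding is 21% (9% to 46%) for half a unit and 63% (22% to 96%) for one unit. If red-cell use did not differ, this bias is absent.

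**What to change.** - Take hemoglobin out of secondary endpoint 2 and base blood loss on the quantitative device measurement described in Study Procedures.
- Report the last available hemoglobin within the 48-hour primary window as its own safety outcome, with arm difference and 95% CI, beside the product count, red-cell units and morbidity results.
- State that hemoglobin speaks to red-cell adequacy only, and refer to the end-of-bleed ROTEM values for the other products.
- Label all of this post hoc, because enrolment closed at 26 and 23. Do not read a non-significant difference as proof of safety.

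The cost is wording and a table row. It needs no new sampling where values within 48 hours are on record; no section schedules such a sample, so missing values should be counted by arm. The downside is that a lower product count may look less favourable if hemoglobin is also lower. No transfusion threshold is proposed or changed.

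### The device measurement of blood loss is not assigned to any endpoint or analysis; secondary endpoint 2 relies on a visual estimate, an EBL with no stated method, and hemoglobin

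*Combined protocol and SAP*

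**What the plan says.** Under Study Procedures: "The investigator will quantitatively measure blood loss during the vaginal or cesarean delivery using a previously validated method". The device is named there as the Triton System.

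Under Secondary Endpoints, item 2: "Intraoperative blood loss (visual estimate in suction canister and sponges, EBL, and pre- vs post-delivery hemoglobin values". The device is not mentioned.

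Under Biostatistical Analysis: "Analysis of variance will be used to compare intergroup demographic data, estimated blood loss (EBL), ROTEM values, and hemoglobin values". This expands the abbreviation EBL and lists hemoglobin as a separate variable. It does not mention the device or say how EBL is obtained.

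Three other statements bear on the point. On masking, Study Procedures says: "The obstetrician, nurse, and anesthesiologist involved in the cases will not be blinded to the study solution assignments". On timing, the same section says: "Eligible and consenting patients who experience PPH will then be randomized". On transfusion, Biostatistical Analysis expects that "we will reproduce the effects of reducing blood product transfusion" and adds that "choice of product transfused with or without the ROTEM protocol will be compared".

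**The concern.** The trial plans one quantitative measurement of blood loss, and the plan never says that this is the blood-loss outcome. Followed as written, endpoint 2 rests on weaker measures, and a reader cannot tell which quantity the EBL comparison tests. With the method open, the choice could also be made after the data are seen.

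Hemoglobin raises a further problem. The intervention is meant to act on transfusion, and red-cell transfusion raises hemoglobin. If one arm received fewer red cells before the post-delivery sample, at the same true loss it would show a larger fall and appear to have bled more. A real reduction in loss in that arm could be hidden.

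The visual estimate is open to bias if the person making it knows the arm. The treating team is unblinded, and the documents do not say who makes the estimate.

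**Working it through.** The plan states no effect size, SD or sample size for blood loss, so there is no figure of its own to reproduce. The check is mainly a comparison of text.

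**Step 1. Where each measure appears.**

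| Measure | Study Procedures | Secondary endpoint 2 | Biostatistical Analysis |
|---|---|---|---|
| Device value | Planned | Not named | Not named |
| Visual estimate | Not named | Listed | Not named |
| EBL | Not named | Listed, no method | Expanded, analysis of variance, no method |
| Hemoglobin | Drawn as a routine lab | Listed under blood loss | Analyzed as a separate variable |

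No row carries the device value from collection through to an endpoint and an analysis.

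**Step 2. What EBL could be.**
- If EBL is the visual estimate, the device value is analyzed nowhere.
- If EBL is the device value, it is analyzed, but the plan does not say so, and the endpoint still counts two weaker measures beside it.
- If EBL is something else, neither the device value nor the visual estimate has a planned analysis.

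The text does not choose between these.

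**Step 3. When hemoglobin misstates loss.** Let k be the rise in hemoglobin per red-cell unit, and g the difference between arms in mean red-cell units given before the post-delivery sample. At identical true loss:

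shift in the arm difference = k × g.

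It is zero if the arms received equal units (g = 0) or if the sample precedes transfusion (again g = 0). Adjusting for pre-delivery hemoglobin does not remove it, because the shift arises after that baseline.

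The documents give neither k nor g nor a hemoglobin SD. As an illustration only, assume k = 1.0 g/dL (range 0.7 to 1.3):
- g = 0: shift 0.
- g = 0.5 units: 1.0 × 0.5 = 0.5 g/dL (0.35 to 0.65).
- g = 1.0 unit: 1.0 g/dL (0.7 to 1.3).

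For scale, the Note at the end of Biostatistical Analysis gives 26 control and 23 ROTEM patients. The 95% confidence half-width for a difference in means is t(0.975, 47 df) × sqrt(1/26 + 1/23) = 2.012 × 0.2863 = 0.576 SD. At assumed SDs of 1.0, 1.5 and 2.0 g/dL this is 0.58, 0.86 and 1.15 g/dL. The shift from a 0.5-unit gap is then 0.5/0.86 = 58% of the half-width at the middle values. Over the assumed ranges of both k and SD it runs from 0.35/1.15 = 30% to 0.65/0.576 = 113%. Every input here except 26 and 23 is assumed, so this shows only that the shift could matter if both conditions held. It does not estimate what happened in this trial.

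**The case against.** The case against has several parts.

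- **EBL.** A reader might infer that EBL is wholly undefined. The documents do not support that: the analysis section expands it and assigns a test. In endpoint 2 it may simply label the visual estimate beside it. What stands is that its method is unstated, and on that reading the device value is still left out.
- **Hemoglobin as a volume.** A reader might infer that the plan turns hemoglobin into blood loss. It does not; the analysis treats it as its own variable. What stands is the grouping in endpoint 2.
- **Actual bias.** A reader might infer that the hemoglobin comparison is biased, or biased against the ROTEM arm. That needs a red-cell difference between arms and a sample drawn after transfusion, and the documents settle neither. The expected reduction concerns blood products in general. A purple-top tube is drawn when hemorrhage is recognized; if that supplied the post-delivery value, much or all of the shift would vanish. The Note reports no effect on the primary outcome. That does not exclude a red-cell difference, because the primary endpoint counts all products together, but it does not show one either.
- **Masking.** The visual estimate has no planned analysis unless EBL is that estimate. The statement "An investigator not involved in the case will conduct ROTEM measurements" concerns the ROTEM assay and says nothing about who estimates loss. The device reader's masking is not stated either, so changing the measure does not cure that problem.
- **Weight.** This is one secondary endpoint in a trial closed to recruitment, and no conclusion in the documents rests on it. That is a fair argument for low severity.

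**Conclusion.** The point holds in a limited form. The quantitative measurement is planned but assigned to no endpoint or analysis, and EBL has a name and a test but no method. Hemoglobin change should not be counted as blood loss where treatment may alter red-cell transfusion.

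The size of any bias cannot be computed from the documents. It is conditional on red-cell units differing by arm and on the sample following transfusion, and without either condition there is none. The primary endpoint, the number of blood products, is unaffected. This is a low-severity, inexpensive improvement.

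**What to change.** - Name the device measurement as the blood-loss measure in secondary endpoint 2 and in Biostatistical Analysis. If EBL is already that value, say so.
- Report the visual estimate descriptively.
- Report post-delivery hemoglobin as its own outcome, adjusted for pre-delivery hemoglobin, with the sample timing and the red-cell units given by arm. Do not present it as a measure of blood loss.
- Because recruitment has ended and the primary result is known, disclose the change as post hoc and also report the measures that endpoint 2 now lists.

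The cost is endpoint and analysis wording plus a disclosure; no new data collection is needed. There are downsides. Device readings may be incomplete, so missing readings should be given by arm. The total may include loss before randomization, since patients are randomized only once hemorrhage has occurred, and the intervention could not affect that part. The switch does not itself mask the person taking the reading, so the report should state whether that person knew the arm.

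### The closing note infers no effect from 49 of a planned 100 patients without an estimate or interval, and the sample-size text contradicts itself on recruitment

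*Combined protocol and SAP*

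**What the plan says.** The primary endpoint is "Number of blood products transfused, t_0 = diagnosis of PPH by criteria defined above", counted to 48 hours after onset.

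The sample-size paragraph of Biostatistical Analysis takes its size from an earlier study of 50 per group and expects that with the same number ("100 patients total), we will reproduce the effects of reducing blood product transfusion"). It claims 80% power at 50 per group and 5% significance, and then adds: "100 subjects per group will be recruited with the goal of completing 50 subjects in the control group and 50 subjects in the ROTEM group".

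Under Subject Enrollment, "subjects will be consented by the principal investigator or physician co-investigator at least two hours prior to the patient's vaginal or cesarean delivery". Under Study Procedures, "Eligible and consenting patients who experience PPH will then be randomized to" the control or ROTEM group.

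On tests, the plan says "Data will be analyzed using one-way analysis of variance and Kruskal-Wallis tests as appropriate", followed by "Analysis of variance will be used to compare intergroup demographic data, estimated blood loss (EBL), ROTEM values, and hemoglobin values".

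The closing Note says that "the study was stopped prior to our goal enrollment of 100 patients (N = 50 per group"). It reports 49 recruited (26 control, 23 ROTEM), gives slow recruitment as the reason, and warns that trials stopped early may overestimate effects. From the lack of impact on the primary outcome it then infers that more recruitment would have led to the same clinical result, namely no effect.

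**The concern.** The main issue is the inference in the Note. A non-significant comparison in about half the planned sample is what one would expect if there were no effect, but it is also a common result when the effect is real and of the size planned for. The estimate and its interval tell these apart, and the Note gives neither. Its one caveat about early stopping, overestimated effects, concerns trials that stop on a favourable result. For a null result the relevant risk is lost power, which the Note does not mention. A reader could take the Note as evidence that ROTEM guidance does not reduce transfusion.

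The second issue is a contradiction. One hundred recruited per group is 200 patients, whereas the preceding sentence and the Note both give 100 in total.

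The third is minor. The 80% power cannot be checked, because the paragraph does not state the difference, SD, sidedness or test behind it.

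**Working it through.** **The plan's own figure.** The 80% at 50 per group can be neither reproduced nor refuted. The inputs given are n = 50 per group, α = 0.05 and power 0.80. Effect, SD and sidedness are not given. The most one can do is solve for the standardised difference d that makes the statement true.

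**Assumptions.** Roughly normal data, equal SDs and a t-test, which for two groups is the one-way analysis of variance that the plan names. Sidedness is shown both ways. The outcome is a count, so results in SD units are approximate.

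**Step 1: difference detectable with 50/50.** Power = P(T > t_crit), where T is noncentral t with n1 + n2 − 2 degrees of freedom and noncentrality d / √(1/n1 + 1/n2). With 98 degrees of freedom and √(2/50) = 0.200:
- two-sided (t_crit 1.984): 80% power at d = 0.566
- one-sided (t_crit 1.661): 80% power at d = 0.501

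**Step 2: the same differences at 26/23.** √(1/26 + 1/23) = √(0.03846 + 0.04348) = 0.2863, with 47 degrees of freedom.
- two-sided (t_crit 2.012): noncentrality 0.566 / 0.2863 = 1.977, power 49.1%. A real difference of this size would give a non-significant result 100 − 49.1 = 50.9% of the time.
- one-sided (t_crit 1.678): noncentrality 0.501 / 0.2863 = 1.749, power 53.2%
- 80% two-sided power at 26/23 needs d = 0.819, which is 0.819 / 0.566 = 1.45 times larger.

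A simulated Kruskal-Wallis test on normal data (10,000 runs, d = 0.566) gave 48% power at 26/23 and 78% at 50/50.

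**Step 3: width of the interval.** The half-width of a 95% interval at 26/23 is 2.012 × 0.2863 = 0.576 SD. An observed difference of exactly zero would therefore have an interval of about ±0.58 SD, which contains 0.57 SD.

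**Step 4: would more recruitment have given the same result?** The relevant quantity is conditional power, which needs the observed Z, and this is not reported. The Z values below are assumed. The information fraction is t = [1 / (1/26 + 1/23)] / [1 / (2/50)] = 12.204 / 25 = 0.488. In the normal approximation the two-sided design difference is 0.560 SD, so the drift is θ = 0.560 × √25 = 2.80. Conditional power = Φ{[Z√t + θ(1 − t) − 1.96] / √(1 − t)}; for the observed trend, θ is replaced by Z/√t.

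| Assumed Z at 49 patients | Under the design difference | Under the observed trend |
|---|---|---|
| 0 | 23% | 0.3% |
| 1 | 60% | 23% |

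The chance of a different final result thus runs from negligible to better than even, depending on data that the Note does not show.

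**Step 5: recruitment figures.** 100 per group × 2 = 200, against 100 in the sentence before and in the Note. Consent is taken before delivery and allocation follows only after PPH, so a number of consented patients cannot be counted by group. If the clause means randomised patients, 100 recruited to complete 50 implies 1 − 50/100 = 50% loss. No loss rate is stated, and the primary endpoint closes at 48 hours.

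**The case against.** Five points can be made on the other side.

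- **The target is not really in doubt.** A reader might infer from the clashing clause that the target could have been either 100 or 200. The documents do not support that: the Note gives 100 (50 per group), the preceding sentence gives 100 in total, and the clause itself distinguishes recruiting from completing. This stands. One clause contradicts the rest and needs correcting, but the randomised goal is settled.
- **The missing effect and SD are not an error.** They may lie in the earlier study on which the paragraph relies. Kruskal-Wallis for the primary count is also a plausible reading, since the analysis of variance list omits that outcome. This largely stands: 80% is arithmetically possible, and the gap is one of reporting.
- **Withdrawal is provided for.** The early endpoints and the adverse-event text allow patients to leave the study. That is true, but neither gives a rate or suggests a loss of half.
- **The power figures are back-solved.** They start from an 80% that cannot be verified, assume normality for a transfusion count, and are not in units of blood products. This stands, so they serve as illustration and should not be required text.
- **A continued null may have been likely.** If the observed difference was near zero, the Note's prediction of another non-significant result could well be right. This stands as a possibility, but predicting non-significance is not the same as showing no effect, and the Note runs the two together.

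**Conclusion.** The inference of no effect is unsupported as written and should be withdrawn. With 49 of 100 patients, power for the difference that 50 per group detects with 80% power falls to about 49% (two-sided) or 53% (one-sided), and even a zero observed difference need not exclude it. These figures assume roughly normal data and a 5% test. The logic does not depend on them: a non-significant result without an estimate and interval does not establish absence of effect.

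A reader might go further and infer that the trial missed a real benefit, or that full recruitment would have reversed the result. The documents do not support either, because the observed difference is not reported and its interval might exclude a relevant reduction.

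The recruitment clause is a genuine internal contradiction, of lesser consequence because the Note settles the randomised goal. The basis of the 80% is a reporting gap; nothing in the documents shows the figure to be false.

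**What to change.** Make a dated correction that leaves the existing text visible.

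1. **Closing Note.** Withdraw the inference of no effect. Report the observed difference in number of blood products with its 95% interval, by a method suited to a count. Describe the result as inconclusive unless the interval excludes a relevant reduction. Name lost power as the main limitation of stopping early with a null result. The power figures above may be added as a retrospective illustration with their assumptions, but this is optional.
2. **Sample-size paragraph, target.** State one randomised target, 100 patients (50 per group), as in the Note. If 100 per group was meant as a consent target, the sponsor should give that number separately and without a group. If it allowed for withdrawals, state the rate assumed.
3. **Sample-size paragraph, power.** Give the effect, SD, sidedness and primary-outcome test behind the 80%, or state that none were specified. Say that the size was chosen to match a previous study of 50 per group, in place of the expectation of reproducing its effects.

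The cost is text and one interval. Recruitment has closed, so no patients are added and conduct does not change. The price to the sponsor is a less definite conclusion.
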